10.1.4 Definition of Subject Cure

Subject Cure: All lesions cured by the end of follow up at Month 7 visit. *Subject Failure:* Not all lesions clinically cured, or a new lesion due to *Leishmania*.

Primary endpoint(s): The co-primary endpoints are the subject cure rate for the modified intention-to-treat (mITT) and evaluable populations.

10.2 Efficacy Assessment of ML Subjects

10.2.1 Assessment Methods

For subjects with suspected ML, an ENT specialist will examine the nasal and oral mucosa. Each of 5 possible sites (nasal skin, nasal mucosa, palate, pharynx, and larynx) will be evaluated for 4 possible signs of disease (erythema, edema, infiltration, and erosion) and graded on a 0-3 scale: 0 = no disease, 1 = mild disease, 2 = moderate disease, 3 = severe disease. If possible, the ENT specialist who first examined the subject will re-evaluate the oral-nasal mucosa at each follow-up visit for the subject

10.2.2 Clinical Parameter and Definition of Clinical Responses

Clinical response will be measured will be a composite score, the mucosal severity score (MSS). The MSS is the sum of the severity scores for each clinical sign at each clinical site of disease. The Maximum MSS is 60: grade 3 severity for each of 4 possible signs at each of the 5 possible sites.

Healed:MSS that is 0 in absolute value [equals 0% of the entrance MSS score].Improved:MSS that is 1%-25% of the entrance MSS score.Non-substantial Change:MSS that is 26%-99% of the entrance MSS score.Worse:MSS >100% of the entrance MSS score.Relapse:MSS substantially increases after initially improving or becoming 0.

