4.2.8.5 Mucosal Leishmaniasis (Soto et al., 2007)

The initial study design was a randomized equivalency study of oral miltefosine (50 subjects) versus standard therapy with pentavalent antimony (25 subjects). Due to changes in regional standard of care to amphotericin B (45 mg/kg as 1mg/kg doses for 45 consecutive days), and due to initial positive response rates in the miltefosine group, subjects refused to be treated with antimony or to be randomized to the amphotericin B arm of the study. Therefore, the final study design became an evaluation of one cohort of 78 subjects who received miltefosine (2.5 mg/kg/day for 28 days). An almost contemporary group of 19 subjects who received amphotericin B (45 mg/kg) as miltefosine treatment was getting organized was evaluated as a *post hoc* comparison group.

Miltefosine was well tolerated. Nausea, vomiting, and diarrhea were each reported by 8–17 subjects. Most episodes were CTC grade 1; one episode was grade 3. Most episodes lasted 1–2 days and a few lasted 3–4 days. Mean values of liver function tests and kidney function tests did not change; a few subjects had values that were slightly above the upper limit of normal after treatment.

Of the 78 subjects who received miltefosine, 72 were evaluable. Fourteen of 19 subjects in the amphotericin B group were evaluable. Fifty-one (71%) of the 72 evaluable miltefosine subjects were "cured" by the definition of >90% diminution in the mucosal severity score with 12 months of follow up. Almost all (49 [96%]) of these subjects demonstrated complete resolution of their

clinical signs. The cure rate for the 36 subjects who had "mild" disease (i.e., affecting only the nasal skin and nasal mucosa) was 83%. The cure rate for the 36 subjects who had more extensive disease (involving the palate, pharynx, and larynx) was 58%.

The cure rate for the amphotericin B group (45 mg/kg over 90 days) was 7 (50%) of 14. Since the historic cure rate for treatment of ML in neighboring Peru varies between 10% and 75%, this study suggests that miltefosine is approximately as effective as standard treatment with antimony, and with amphotericin B, for Andean mucosal disease. Before-and-after photographs of one subject from this study with involvement of the external nares (**Figure 1**), illustrates the clinical improvement in skin and mucosa consequent to successful miltefosine therapy.

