10.1.2 Definitions of Lesion Response

Healed:	100% reduction in lesion area [lesion size = $0x0 \text{ mm}^2$]
Improved:	50% - 99% reduction in lesion area
No change:	49% enlargement to 49% reduction in lesion area
Worse:	>50% enlargement of lesion area at or after the end of therapy.
Relapsed:	Substantial enlargement of lesion after initial improvement or healing.

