10.2.3 Definition of Subject Responses

Subject cure: Clinical cure is lesion is healed.

Subject failure: Leasion did not heal. NOTE: The intended response to therapy is a progressive diminution in signs and symptoms and no relapse. Subject failure is defined as clinically worse at the Week 6 visit or thereafter, OR does not improve at the Month 3 or month 7 visits, OR is not healed at the Month 13 visit, OR relapses.

Primary endpoint(s): The primary endpoints are the clinical cure rates for the mITT and evaluable population.

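### The ML Improved band contains no attainable score when the entrance MSS is 1, 2 or 3, so falls from 2 to 1 and from 3 to 1 are labelled Non-substantial Change and may count as failure

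*Combined protocol and SAP*

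**What the plan says.** Section 10.2.1 describes the ML examination: "Each of 5 possible sites (nasal skin, nasal mucosa, palate, pharynx, and larynx) will be evaluated for 4 possible signs of disease". Each sign is "graded on a 0-3 scale", with the grades "0 = no disease, 1 = mild disease, 2 = moderate disease, 3 = severe disease". Section 10.2.2 builds the score: "The MSS is the sum of the severity scores for each clinical sign at each clinical site of disease". It gives the maximum as 60.

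Section 10.2.2 then sets the response categories. Healed is a score of 0. Improved is "MSS that is 1%-25% of the entrance MSS score". Non-substantial Change is 26% to 99% of the entrance score, and Worse is above 100%.

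Section 10.2.3 equates subject cure with healing. It also lists conditions, joined by OR, any one of which makes the subject a failure. One of them reads "OR does not improve at the Month 3 or month 7 visits". The cure rates in the mITT and evaluable populations are the ML primary endpoints. Section 12.7.2 plans to report the proportion of subjects with improvement at each time point.

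The inclusion criteria in 7.1.2 require a parasitological diagnosis and set no minimum entrance MSS. No section gives a rule for small scores.

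**The concern.** A percentage band has been laid over a whole-number score. At low entrance scores the steps between attainable values are wider than the band, so a subject can lose half or two thirds of the score and still not be Improved. The only response that escapes Non-substantial Change at those scores is complete healing.

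This would not matter much if the category were only a label. Section 10.2.3, however, makes lack of improvement at Month 3 or Month 7 a route to subject failure, and failure bears on the primary endpoint. A subject who heals steadily but has one point left at Month 3 could therefore be counted against the drug because of the scale. In addition, the proportion improved planned in 12.7.2 is zero by construction for anyone entering with a score of 1 to 3.

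**Working it through.** **Inputs.** Five sites, four signs, whole-number grades 0 to 3 (10.2.1); the MSS as their sum, and the category bands (10.2.2); the failure list (10.2.3).

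**The plan's own figure.** Maximum MSS = 5 sites x 4 signs x grade 3 = 60. This matches 10.2.2 and confirms that the MSS takes whole-number values from 0 to 60.

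**Condition for the band to be attainable.** Let E be the entrance MSS and m a later non-zero score. Improved requires m of at least 1 and m no more than 0.25 x E. Together these require E of at least 1 / 0.25 = 4. The lower limit of 1% never binds, because even 1/60 is 1.7%.

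**Low entrance scores, with m at or below E:**

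| E | Non-zero m, as % of E | Improved | Non-substantial Change |
|---|---|---|---|
| 1 | 1 (100%) | none | none |
| 2 | 1 (50%), 2 (100%) | none | 1 |
| 3 | 1 (33%), 2 (67%), 3 (100%) | none | 1, 2 |
| 4 | 1 (25%), 2 (50%), 3 (75%), 4 (100%) | 1 | 2, 3 |

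Running through every entrance score from 1 to 60 shows that the band is empty at exactly 1, 2 and 3. Rounding the percentages to whole numbers does not change this.

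**Who is affected.** At E = 1 the only lower score is 0, which is Healed, so nobody improves without healing and nobody is misclassified. The affected falls are at E = 2 and E = 3.

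**Carrying it into 10.2.3.** Take scores of 3, 1, 0, 0 at entry, Month 3, Month 7 and Month 13.

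- Month 3: 1/3 = 33%, Non-substantial Change. If the clause refers to the Improved category, a failure condition is met.
- Month 13: MSS 0, Healed. Under the cure sentence of the same section, the subject is cured.

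The section thus gives both results for one subject. By contrast, a fall from 40 to 10 at Month 3 is 10/40 = 25%, which is Improved, and no failure condition is met at that visit.

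**Effect of the proposed rule.** Improved would mean m above 0, below E, and either no more than 0.25 x E or no more than 1.

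- E = 1: no m lies above 0 and below 1, so nothing changes.
- E = 2: m = 1 becomes Improved.
- E = 3: m = 1 becomes Improved; m = 2 does not.
- E of 4 or more: m = 1 is already within 25%, so nothing changes.

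Only 2 to 1 and 3 to 1 move.

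**The case against.** The strongest objection is to the failure step. Section 10.2.3 writes the word improve in lower case, just after describing a steady decline in signs and symptoms. In 10.3 the cutaneous (CL) sentence capitalises the word and the ML sentence does not. On a plain-language reading any decrease is an improvement, and 3 to 1 at Month 3 is not a failure. That reading is not excluded. The category reading is more natural, because the neighbouring conditions (worse, healed, relapse) are all categories defined in 10.2.2, and because a score labelled Non-substantial Change sits badly with having improved. Two analysts could still score the same subject differently.

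Second, the cure sentence makes 3, 1, 0, 0 a cure, so a wrong primary result is not certain. This stands. The conflict between cure and failure is also wider than small scores: 40, 15, 0, 0 meets it too, since 15/40 = 37.5%.

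Third, the study is single-group and descriptive, with no formal sample size (12.1, 12.3), and 12.7.1 reports MSS components, totals and changes for each subject. An affected course would be visible and could be reclassified. This lowers the stakes but does not supply the missing rule.

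Fourth, the proposed rule lets a one-grade change in one sign count as Improved, and 10.2.1 asks for the same examiner only where possible. That is a real cost of the change.

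Two stronger inferences are not supported. A reader might take the background ML series in 4.2.8.5, where 36 of 72 evaluable subjects had mild disease, to mean that half of ML subjects are exposed. Mild there means "affecting only the nasal skin and nasal mucosa", which is a definition by site; two sites x four signs x grade 3 allows an MSS of up to 24. A reader might also set the ML band against the CL definition of Improved, "50% - 99% reduction in lesion area". That contrast concerns the chosen 75% threshold, which applies at every entrance score (60 to 20 is also 33%), and not small scores.

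**Conclusion.** The gap is real and narrow. That no score is attainable in the Improved band at entrance MSS 1, 2 and 3 follows from the plan's own definitions and needs no assumption. The practical harm is confined to entrance scores of 2 and 3.

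The step to subject failure assumes that improve in 10.2.3 means the Improved category. Even then, the final classification is at stake only for subjects who reach 0 at Month 13, because anyone not healed by then is a failure regardless. For those subjects 10.2.3 contradicts itself, so it would be too strong to say that the plan definitely counts them as failures.

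The number affected cannot be estimated. The documents give no distribution of entrance MSS and no expected number of ML subjects; the 10 to 20 subjects per year in 7.1.1 cover CL and ML together. A reader might also infer that the label forces withdrawal and rescue treatment. Section 10.3 leaves that to the Treating Physician, so the documents do not support it.

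The point should be corrected because a stated rule can give a wrong result and the correction is cheap.

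**What to change.** For the efficacy analysis:

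- In 10.2.2, define Improved as an MSS above 0, below the entrance score, and either no more than 25% of the entrance score or no more than 1 point.
- In 10.2.3, state that improve means this category (or Healed), and reconcile the cure sentence with the failure list so that one subject cannot be both a cure and a failure.
- In 12.7.2, apply the same definition to the proportion improved.

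The withdrawal wording in 10.3 repeats the ML failure conditions but names Month 6 where 10.2.3 names Month 7. The sponsor should reconcile the two; no clinical rule is proposed here.

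The cost is one sentence in 10.2.2 and short clarifications elsewhere, with no new data. The downside is that a one-point fall (2 to 1) or a two-point fall (3 to 1) counts as Improved.

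While 10.2.2 is open, two neighbouring gaps could be closed: a score of exactly 100% of entrance falls in no category, and ratios between 25% and 26% (for example 7/27 = 25.9%) are unclassified unless a rounding rule is stated. The change above does not address either.

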10.2.3 Definition of Subject Responses

Subject cure: Clinical cure is lesion is healed.

Subject failure: Leasion did not heal. NOTE: The intended response to therapy is a progressive diminution in signs and symptoms and no relapse. Subject failure is defined as clinically worse at the Week 6 visit or thereafter, OR does not improve at the Month 3 or month 7 visits, OR is not healed at the Month 13 visit, OR relapses.

Primary endpoint(s): The primary endpoints are the clinical cure rates for the mITT and evaluable population.

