10.1.3 Definition of Clinical Responses

Lesion Cure: Lesion is healed at the Month 7 visit.

Lesion Failure: Each lesion will be considered a failure if it does not meet the criteria for cure (missing data will be considered failures). The intended response to therapy is a progressive diminution in lesion size and no relapse. Lesion failure therefore is defined as clinically worse at the end of therapy or thereafter, OR does not improve at the Week 6 or Month 3 visit, OR is not healed at the Month 7 visit, OR relapses.

NOTE: Parasitological responses can assist the clinician in evaluating the clinical response of the lesion. If the Treating Physician has parasitologically re-investigated a slowly responding lesion

at time-points greater than 2 weeks after the end of therapy, and parasites are still present by microscopy or culture, the physician may interpret the data as indicating therapeutic failure. Note that the presence of parasites prior to 2 weeks after the end of therapy should not be interpreted. Note that because PCR is more sensitive than microscopy or culture on which the clinical experience in the literature is based, PCR positivity post therapy cannot easily be interpreted.

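### ML subject cure and failure overlap in 10.2.3, as do CL lesion cure and failure in 10.1.3, and the text supplied does not say which definition prevails

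*Combined protocol and SAP*

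**What the plan says.** **ML.** Section 10.2.3 gives cure as "Clinical cure is lesion is healed", with no visit named and no condition on the earlier course. Failure then appears in two forms. The short form is "Leasion did not heal". The long form, inside a NOTE, is "Subject failure is defined as clinically worse at the Week 6 visit or thereafter", then "OR does not improve at the Month 3 or month 7 visits", then two further alternatives: not healed at Month 13, or relapse. Section 10.2.2 supplies the categories. Healed is an MSS of 0, Improved is "MSS that is 1%-25% of the entrance MSS score", and Worse is "MSS >100% of the entrance MSS score". Relapse is a substantial rise after improvement or healing, with no threshold for substantial. The ML cure rates in the mITT and evaluable populations are primary endpoints.

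**CL.** In 10.1.3, lesion cure is "Lesion is healed at the Month 7 visit". Lesion failure is first any lesion that does not meet cure. It is then a list joined by OR: worse at the end of therapy or later, no improvement at Week 6 or Month 3, not healed at Month 7, or relapse. Section 10.1.2 defines Worse as ">50% enlargement of lesion area at or after the end of therapy". At subject level, 10.1.4 requires all lesions to be cured by Month 7 and counts as failure any subject short of that or with a new leishmanial lesion. The CL subject cure rates in the two populations are co-primary.

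**Analysis.** Section 12.6.2 tabulates lesions and subjects cured and failed. Section 12.7.2 tabulates ML cure, improvement, failure and relapse at each time point. Sections 12.2, 12.6.3 and 12.7.3 cover populations and missing data. None of these ranks one outcome over another. Withdrawal for lack of efficacy is optional (10.3), so a subject who meets an interim criterion can stay to the final visit. Section 14 says that a SAP will be prepared; no separate SAP is among the documents.

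**The concern.** Cure and failure should divide the analysed subjects into two groups without overlap. Here the short form of failure does that, and the long form does not, because it adds events that can occur before the final visit and be followed by healing. A subject with such a course has two results on the ML primary endpoint, and a CL lesion with such a course has two results in the lesion table.

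The study is open-label with a single group. If the choice between the forms is left until the data are in, it can be made with the affected subjects' outcomes in view. Section 12.6.3 itself notes that errors of interpretation here are not balanced by a comparator group.

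**Working it through.** The documents state no target cure rate, power or precision, so there is no plan figure to reproduce. The check applies the definitions as written.

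1. **ML, overlap on any reading.** Entry MSS 10, Week 6 MSS 11, Month 13 MSS 0.
   - Week 6: 11/10 = 110% of entry, above 100%, so Worse, and a failure on the long form.
   - Month 13: MSS 0, so Healed. This is a cure, and not a failure on the short form.
2. **ML, overlap only if improvement means the defined category.** Entry MSS 10, Month 3 MSS 3, Month 13 MSS 0.
   - 3/10 = 30%, outside the 1%-25% band, so not in the Improved category although the score has fallen by 70%.
   - From an entry score of 10, scores 1-2 (10%-20%) are Improved and scores 3-9 (30%-90%) are not. The reading therefore decides 7 of the 9 possible nonzero decreases.
3. **CL lesion, overlap on any reading.** 20 x 20 = 400 mm² at entry, 25 x 25 = 625 mm² at Day 28, 0 x 0 at Month 7.
   - (625 - 400)/400 = 56%, above 50%, so Worse at the end of therapy and a lesion failure.
   - Healed at Month 7, so a lesion cure. If this is the subject's only lesion, 12.6.2 reports 1/1 cured and 1/1 failed.
4. **CL lesion, overlap only on the category reading.** 400 mm² at entry, 16 x 15 = 240 mm² at Week 6, 0 x 0 at Month 7.
   - (400 - 240)/400 = 40% reduction, which falls in No change.
5. **Breadth of the overlap.** With four categories (Healed, Improved, No or non-substantial change, Worse) at the three visits before the final one, 4³ = 64 patterns end healed. The counts are the same for ML subjects and CL lesions.
   - Worse at one or more of those visits: 4³ - 3³ = 64 - 27 = 37 patterns overlap.
   - Adding no improvement on the category reading: 64 - (3 x 2 x 2) = 52 overlap.
   - Adding relapse, taken as any move to a worse category after Improved or Healed (an assumption, since substantial is undefined): 57 overlap and 7 are cure only.

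   These count patterns. They are not expected frequencies.
6. **Size per subject.** Planned total (7.1.1): 10 x 1 = 10 to 20 x 5 = 100. One reclassified subject moves the rate by 1/10 = 10 points, 1/20 = 5 points or 1/100 = 1 point. CL and ML are reported separately and the split is not given, so the shift within either group is at least this large.

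**The case against.** The strongest reply is that the long list is plainly meant to govern. It carries the words of definition, it already includes not being healed at the final visit, it follows a statement that the intended response includes no relapse, and 10.3 uses nearly the same list as the basis for lack of efficacy. On that view, cure is healing without any of those events. This is a reasonable reading and may be what was intended. It remains an inference: the short form stands just before the list, no section gives the list priority, and for CL both 10.1.4 and the abstract point towards final status.

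A second reply is that the study is descriptive, with no formal sample size, and that lesion areas, lesion responses and MSS will be summarised by visit (12.6.1, 12.6.2, 12.7.1). Much reclassification would be possible from that output. This limits the harm, but it does not settle the headline rate.

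Three stronger inferences are tempting and are not supported.
- *The CL co-primary subject rate is equally contradictory.* Section 10.1.4 builds it on lesions cured by Month 7, so it moves only if an interim lesion failure is carried up to the subject.
- *A new leishmanial lesion makes any subject both cured and failed.* If the new lesion is unhealed, not all lesions are cured and the subject is simply a failure. Overlap needs a new lesion that has itself healed by Month 7, or a reading of all lesions as the original ones.
- *Rescued subjects have no mITT status.* Section 8.8 places other antileishmanial drugs off-protocol, and a missing final measurement already counts as failure (12.6.3, 12.7.3). The gap is confined to a rescued subject who still has a final measurement. That is possible, because 8.6 asks subjects who withdraw in follow-up to return for lesion measurements.

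**Conclusion.** The definitions are wrong as written for ML subjects (10.2.3) and CL lesions (10.1.3): followed literally, they give contradictory results for a course of interim worsening or relapse and then healing. For non-improvement, the overlap depends on whether the word refers to the defined Improved category, which the text does not settle. Only the CL wording in 10.3 capitalises it.

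The effect is 1 to 10 points per affected subject for totals of 100 down to 10, and at least that within CL or ML. The number affected cannot be derived. Table 1 of the protocol records doubling of lesion size and relapse in miltefosine recipients. Table 3 shows healing rising from 15/44 (34%) at the end of treatment to 36/41 (88%) at six months. So both interim failure and late healing occur, but the documents do not say how often they occur in the same subject. A reader might take the 57 of 64 patterns to mean that most healed subjects would be doubly classified; it does not show that.

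The conclusion rests on the text supplied. The SAP announced in section 14 may contain a rule that cannot be seen here. Because the aim is to record efficacy descriptively, with no decision threshold, this should be fixed before analysis but does not undermine the study.

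**What to change.** Before analysis, state one classification rule in 10.1.3-10.1.4 and 10.2.3, and carry it into 12.6.2, 12.7.2 and the SAP. It should name the final visit (Month 7 for CL, Month 13 for ML) and make failure the exact complement of cure in the mITT population, keeping the existing missing-as-failure rule. Two rules would do this:

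- (a) healing at the final visit alone decides; or
- (b) cure is healing at the final visit with no interim failure criterion met and no relapse.

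Report the other rule as a sensitivity analysis and list every subject and lesion classified differently. Also state:

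- whether no improvement means failure to reach the defined Improved category;
- what rise counts as substantial for relapse, since one of the two analyses will need it;
- how the mITT analysis counts a subject who had rescue treatment off-protocol but still has a final measurement;
- how it counts a CL subject whose new leishmanial lesion has healed by Month 7.

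For ML non-improvement, 10.3 names Month 6 where 10.2.3 names Month 7. These passages must be reconciled with each other and with the schedule.

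The cost is a short text change, one table and one listing, all from visit data already scheduled. Each rule has a price. Rule (a) counts late or spontaneous healing after an interim failure as cure, which matters in an uncontrolled study of a disease that 4.1.3 describes as often self-healing in its cutaneous form. Rule (b) counts slow responders as failures. The sensitivity analysis shows the reader how much this matters.
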